### **Protocol Synopsis**

Title	Treatment of Post-Operative Pain Following Orthopedic Surgery with SPRINT® Peripheral Nerve Stimulation (PNS) System in a Randomized, Double-Blinded, Placebo-Controlled Trial
Device (510k Cleared)	The SPRINT® Peripheral Nerve Stimulation (PNS) System
Study Design	Randomized, Double-Blinded, Placebo-Controlled, Multicenter Post Market Study
Primary Study Objective	The study objective is to gather data on the use of the PNS therapy for the treatment of postoperative pain following orthopedic surgery. The study will compare the responses of two groups.
Study Plan	Individuals must have persistent, average pain score of ≥ out of 10 following surgery to qualify Individuals who have undergone primary, unilateral or bilateral total knee replacement (TKR)/revision (PKR) and report unilateral postoperative pain (≥ on an 11-point numerical rating scale on the Brief Pain Inventory Short Form (BPI-SF Question #5)) will be considered for enrollment into the study. After informed consent is obtained, potential subjects will be evaluated for general eligibility. The individuals who satisfy the preliminary criteria will be asked to complete an assessment of baseline pain to determine if their postoperative pain is persistent.  Percutaneous leads will be placed to target the nerves
	innervating the region of pain  Qualifying subjects will be randomized to either Group #1 (Treatment) or Group #2 (Control). In all subjects, leads will be placed  All subjects will be instructed to use the SPRINT Stimulator  during the 8-week treatment period. In Group #1, the system will deliver active electrical stimulation, while in Group #2, the system will deliver sham (placebo) stimulation during the 8-week treatment period.  After lead removal, Group #1 subjects will be followed for 12 months from the start of treatment (SOT).
	Group #2 will be given the option of crossing over Following the completion of a follow-up visit  Group #2 subjects will be given the option of crossing over to receive active stimulation. If subjects do not choose to receive active stimulation, they will be discharged from the study. If subjects choose to receive active stimulation, leads will again be placed

Sites (N)	Up to 15 sites
Subjects (N)	Up to subjects will be randomized
Inclusion Criteria	At least 21 years old
(assessed at Eligibility Visit 1)	
 
Underwent a 1. Primary total knee replacement (TKR), 2. Secondary/revision TKR or 3. Partial/unicompartmental knee replacement (PKR)
 

	
 
Knee pain directly resulting from knee replacement surgery in affected knee ≥  on a scale of 0-10 (BPI-SF, question #5)
 

	
 
Able to understand and provide written consent
 
Able to comply with all study requirements (e.g., if needed, has a caregiver to assist)
 

Exclusion Criteria (assessed at Eligibility Visit 1)	Change of prescribed medications affecting knee pain within the past 4 weeks
	Current high opioid use (i.e., mg oral MED in a single day)     If subject reports any opioid use within the past 4 weeks subject must not have used opioids daily for the month preceding knee replacement.
	If subject reports any opioid use within the past 4 weeks     subject must not have used mg     oral MED on any day during the month preceding knee     replacement
	Body Mass Index (BMI) > 40 kg/m²
	Compromised immune system based on medical history     or other conditions that places the
	subject at increased risk in the opinion of the investigator
	
 
History of valvular heart disease
 
Deep brain stimulation (DBS) system, an implanted active cardiac implant, or any other implantable neurostimulator whose stimulus current pathway may overlap the SPRINT Stimulator's current pathway.
 

	
 
History of bleeding disorder (e.g., hemophilia) or subjects with active anticoagulation whose use or temporary modification for the lead placement procedure places the subject at increased risk in the opinion of the investigator.
 

	
 
Confounding conditions
 
Diagnosis of Diabetes Mellitus Types I or II
 

	
 
History of nerve damage in the affected leg
 
Confirmed tape or adhesive allergy.
 
Contraindications to the proposed anesthetic protocol
 
Any other condition that may interfere with the ability to participate in a clinical trial 
 
as determined by the Investigator
 
Prisoners, minors, or individuals that report to investigators (e.g., students, employees)
 
History of substance abuse
 
Potential secondary gain issues related to knee pain (e.g., pending claims or receiving disability)
 
Botulinum toxin injection in the affected limb
 
Steroid injection in the past 30
 
 
 

	
 
days
 
Subject has participated in previous SPR Therapeutics sponsored study
 

Additional Inclusion Criteria (assessed before randomization)	
 
baseline pain: Average pain intensity score of ≥ (determined by calculating the mean "average pain" collected in a 7-day diary, using Question #5 on the BPI-SF; mean score must be ≥ ).
 
Persistent baseline pain: Rating of average pain intensity over past week (BPI-5) remains persistent for two consecutive weeks and is ≥ .
 

Additional Exclusion Criteria (assessed before PNS)	Pregnant (either urine dipstick or serum in females of reproductive potential)
Primary Safety Endpoint	Occurrence and type of study-related adverse events
Primary Clinical Endpoint	Pain Intensity: All subjects will record daily pain scores for the affected leg in diaries using BPI-SF Question #5. The percent change in pain scores will be determined for each subject by taking the mean of the daily average pain intensity (BPI-SF Question #5) reported in the baseline diaries compared to the mean score reported over Weeks 5-8 of the treatment period (i.e. the average of all diary scores during this

	period). Data will be collected as described in the Schedule of Procedures (Appendix A).
Secondary Endpoints	
 
Average pain (BPI-SF Question 5)
 
Pain Medication usage
 
Pain Catastrophizing Scale (PCS)
 
Patient Global Impression of Change (PGIC)
 
Pain Interference (BPI-9)
 
Western Ontario McMaster Universities Osteoarthritis Index (WOMAC)
 
Six Minute Walk Test (6MWT)
 

Exploratory Analyses	• ON THIRD PAGE (ONTY)

### 1.0 General Information

### 1.1 Title of the Investigation

Treatment of Post-Operative Pain Following Orthopedic Surgery with SPRINT® Peripheral Nerve Stimulation (PNS) System in a Randomized, Double-Blinded, Placebo-Controlled Trial

### 1.3 Name of the Device

The SPRINT® Peripheral Nerve Stimulation (PNS) System

### 1.4 Indication for Use

The SPRINT PNS System is 510(k) cleared with the following Indication for Use.

The SPRINT Peripheral Nerve Stimulation (PNS) System is indicated for up to 60 days for:

- Symptomatic relief of chronic, intractable pain, post-surgical and post-traumatic acute pain;
- Symptomatic relief of post-traumatic pain;
- Symptomatic relief of post-operative pain.

The SPRINT PNS System is not intended to treat pain in the region innervated by the cranial and facial nerves.

### 1.5 Study Objective

The objective of this study is to gather data on the use of the PNS therapy for the treatment of postoperative pain following orthopedic surgery. The study will compare the responses to active stimulation vs. sham stimulation.

### 1.6 Funding

The proposed study is funded by the sponsor and supported in part by the Department of Defense (DoD) U.S. Army Medical Research and Materiel Command, Congressionally Directed Medical Research Programs, Peer Reviewed Orthopedic Research Program-Clinical Trial Award W81XWH-17-PRORP-CTA. The contract number is W81XWH-18-1-0799.

### 2.0 Background and Justification for the Design of the Clinical Investigation

# 2.1 Postoperative pain following orthopedic surgery is a substantial medical problem

Postoperative pain following orthopedic surgeries such as bone fracture repair (e.g., open reduction internal fixation), amputation, limb salvage, and joint replacement (e.g., knee replacement), is moderate to severe in up to 90% of patients, and acute postoperative pain if uncontrolled can become chronic pain and last for several months to years[1-25]. Postoperative pain is treated using opioids and other oral medications, which can result in misuse and debilitating side effects. The side effects of opioids (e.g., sedation, dizziness, nausea, constipation, urinary retention, sleeping problems) often interfere with function, activities of daily living, and physical rehabilitation[7, 26-31]. Also, patients following orthopedic surgery often use opioids for several weeks following surgery: the median time to cessation of opioids is approximately 1-2 months, and approximately 30% of patients are still on opioids at 90 days following surgery[32-35]. Such long-term use of opioids increases the risks of dependence, use of illicit substances (e.g., heroin), overdose, and death[30, 36, 37].

Following orthopedic surgery, pain is one of the primary sources of disability that limit return to normal function [38-40]. For example, when traumatic injury results in amputation, pain rather than the loss of the limb is frequently what most impacts function, preventing completion of simple daily activities, and correlating most negatively with return to employment [38, 41, 42]. In addition, pain inhibits rehabilitation, preventing optimal recovery and the restoration of physical function [43-46]. Poor functional outcomes following bone fracture repair surgery, amputation, limb salvage, and joint replacement can persist for  $\geq 1$  year following surgery in 25-50% of patients, resulting in high rates of medical separation from service in the military and failure to return to work [12, 47-56].

Electrical stimulation has been used successfully to treat chronic pain, avoiding many of the debilitating side effects associated with medications[57-60]. However, electrical stimulation is rarely used to treat postoperative pain because of major limitations of existing methods. Transcutaneous electrical nerve stimulation (TENS) is seldom successful in treating postoperative pain because the required stimulation intensities to activate the deep pain-relieving fibers[61, 62] can irritate the skin and activate cutaneous nerve endings, causing discomfort and/or pain[63-65]; and low (comfortable) intensities are ineffective[58, 66-75]. Traditional methods of stimulation can reduce chronic neuropathic pain but require invasive surgery for system implantation. Spinal cord stimulation and conventional methods of peripheral nerve stimulation can activate nerve fibers from both superficial and deep tissues of the regions of pain by stimulating spinal/peripheral nerves with implanted electrodes, avoiding the intolerable cutaneous discomfort of TENS. However, these fully implanted systems require invasive surgery to place the electrodes and the stimulator. As a result, they are highly unsuitable as a temporary therapy for patients who have recently undergone major surgery.

Percutaneous peripheral nerve stimulation (PNS) is a temporary, non-surgical, and minimally-invasive therapy that is designed to overcome the barriers associated with traditional neurostimulation modalities. In this therapy, a fine wire open-coil lead is placed percutaneously to target peripheral nerves that innervate the region of postoperative pain. Percutaneous PNS enables selective stimulation of pain-relieving fibers and avoids unwanted muscle contractions, muscle weakness, and reduced proprioception to facilitate physical rehabilitation and accelerate functional recovery. The therapy is delivered using percutaneous open-coil leads designed for up to 60 days of PNS with minimal risk of infection.

Because the lead is placed percutaneously, the approach can activate target nerve fibers while avoiding cutaneous discomfort. Also, this approach does not require invasive surgery to implement and can be delivered quickly without specialized training.

The goal of this randomized-controlled trial is to gather data on the use of the SPRINT PNS therapy for the treatment of postoperative pain following orthopedic surgery.

[figure not shown]
# 2.2 Percutaneous PNS has been tested to treat pain in patients following orthopedic surgery in prior studies.

Ten subjects that had undergone TKR and were experiencing postoperative pain were enrolled. Of these subjects, 6 subjects were tested between postoperative day (POD) 6-14, and 4 subjects were tested between POD 40-100. The femoral and/or sciatic nerves were targeted using leads placed percutaneously, and the target nerve(s) were selected based on the location of pain (e.g., front or back of the knee). Leads targeting the femoral nerve were placed by inserting the introducer needle distal to the femoral crease and lateral to the femoral nerve, while leads targeting the sciatic nerve were placed using a trans-gluteal or popliteal approach. Stimulation amplitude and pulse duration were adjusted to provide comfortable sensations covering the regions of pain. Subjects rated their "Pain Right Now" on the Brief Pain Inventory Short Form (Question 6, BPI-6) with stimulation off and stimulation on. In 9 subjects (90%), pain at rest was reduced by a highly clinically significant amount (≥50%) with stimulation on (mean=1.4) compared to stimulation off (mean=5.4), with an average reduction of 75%. All leads were removed without discomfort or complication in a brief, out-patient procedure (i.e., subjects did not take stimulation system home).

In another prospective case series study, subjects underwent lead placement 0-14 days prior to total knee replacement and received PNS following surgery for up to 6 weeks. Postoperatively at 1 month following surgery, the average pain over the previous week was mild and well-controlled ( $\leq$ 4/10) in 15/18 subjects (83%). Fourteen of 18 subjects (77%) had ceased opioid use by 62 days following surgery (*i.e.*,  $\leq$ 25% of subjects still using opioids). At 3 months following surgery, 17 subjects (94%) had pain of  $\leq$  2/10, and 16 subjects (89%) had ceased opioid use. Overall, these results compared favorably to historical controls: persistent pain of  $\geq$ 3 months after TKR is typically reported in 10-20% or more of patients[3, 8, 20, 24, 76, 77], and

25-40% of patients continue to use opioids at 90 days (3 months) after TKR[ $\underline{34}$ ,  $\underline{78}$ ,  $\underline{79}$ ].

3.0 Device Description This study utilizes the commercially available SPRINT® PNS System. Electrical stimulation will be applied via leads in the affected limb

### 4.0 Study Design

### 4.1 General Overview

This study is a post-market randomized, double-blinded, placebo-controlled, multi-center study to gather post-market data on the use of peripheral nerve stimulation (PNS) therapy for the treatment of post-surgical pain following orthopedic surgery (*i.e.*, knee replacement). The treatment of post-surgical pain is included in the indication statement for the SPRINT® PNS System (K181422; K202660; K211801).

### 4.2 Study Population

Prospective subjects will be screened for eligibility into the study using the Eligibility criteria listed in 4.2.1.

### 4.2.1 Selection Criteria

Individuals who meet all of the inclusion and none of the exclusion criteria will be eligible to enroll in the study as subjects.

### 4.2.1.1 Inclusion Criteria

- 1. At least 21 years old
- 2. Underwent a
  - a. Primary total knee replacement (TKR),
  - b. Secondary/revision TKR or
  - c. Partial/unicompartmental knee replacement (PKR)
- 3. Knee pain directly resulting from knee replacement surgery in affected knee ≥ on a scale of 0-10 (BPI-SF, question #5)
- 4. Able to understand and provide written consent
- 5. Able to comply with all study requirements (e.g., if needed, has a caregiver to assist)

### 4.2.1.2 Additional inclusion criteria (assessed prior to randomization)

- baseline pain: Average pain intensity score of ≥ (determined by calculating the average pain collected in a 7-day diary, using Question #5 on the BPI-SF)
- 2. Persistent pain following a knee replacement as assessed using weekly recall average pain intensity scores.

### 4.2.1.3 Exclusion Criteria

- 1. Change of prescribed medications affecting knee pain within the past 4 weeks
- 2. Current high opioid use (i.e., mg oral MED in a single day)
- 3. If subject reports any opioid use within the past 4 weeks subject must not have used opioids daily for the month preceding knee replacement
- 4. If subject reports any opioid use within the past 4 weeks subject must not have used mg oral

	MED on any day during the month preceding knee replacement
5	Body Mass Index (BMI) > 40 kg/m 
	Compromised immune system based on medical history
0.	
	or other conditions that places the subject at increased risk in the opinion of the investigator
7.	History of valvular heart disease
	Deep brain stimulation (DBS), an implanted active cardiac implant, or
	any other implantable neurostimulator whose stimulus current pathway
	may overlap the SPRINT Stimulator's current pathway.
9.	History of bleeding disorder (e.g., hemophilia) or subjects with active
	anticoagulation whose use or temporary modification for the lead
	placement procedure places the subject at increased risk in the
40	opinion of the investigator.
10	Confounding conditions
11	Diagnosis of Diabetes Mellitus Types I or II
	History of nerve damage in the affected leg
12	Thistory of herve damage in the unested log
13	Confirmed tape or adhesive allergy
	Contraindications to the proposed anesthetic protocol
15	Any other condition that may interfere with ability to participate in a
	clinical trial
	as determined by the
	Investigator
16	Prisoners, minors, or individuals that report to investigators (e.g.,
4-	students, employees)
	History of substance abuse
18	Potential secondary gain issues related to knee pain (e.g., pending
10	claims or receiving disability)  Botulinum toxin injection in the affected in the affected
19	limb
20	Steroid injection
21.	Subject has participated in any drug or device trial in the past 30 days. Subject has participated in previous SPR Therapeutic sponsored study
	Changaraa ciilay

## 4.2.1.4 Additional exclusion criteria (assessed before lead placement)

 Pregnant (either urine dipstick or serum in females of reproductive potential)

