### 4.3 Sample Size and Justification

Up to 15 sites will participate in this study. Up to individuals will be enrolled as subjects and randomized to either Group #1 or Group #2. Subjects will be randomized at the start of Visit 2, after final eligibility is verified and before lead placement procedures begin.

Subjects who sign an informed

consent form and do not meet all study eligibility criteria will be considered screen failures and not count against the number of enrolled subjects.

4.4 Study Endpoints	4.4	Study	Endp	oints
---------------------	-----	-------	------	-------

Outcome measures will be collected from each subject in Group #1 (8 weeks of active stimulation) and Group #2 (8 weeks of sham stimulation) at Baseline and at specified follow-up visits

To support the study endpoints, the following outcome measures will be used:

- 1. Brief Pain Inventory, Short Form (BPI-SF)
- 2. Diary
  - Average affected Knee Pain (rated using BPI Question 5)
  - Medication affecting pain, including reason for use
- 3. Western Ontario McMaster Universities Osteoarthritis Index (WOMAC)
- 4. Patient Global Impression of Change (PGIC)
- 5. Pain Catastrophizing Scale (PCS)
- 6. 6 Minute Walk Test (6MWT)

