### 5.2 Visit 2: Lead Placement and Testing (Day 0)

Following the baseline visit, individuals who qualify for lead placement (i.e., meet the additional inclusion and exclusion criteria) will return to the clinic for placement of the percutaneous leads.

[figure not shown]

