# 5.2.1 Randomization Qualifying individuals will be randomized to either Group #1 (Treatment) or Group #2 (Control) using block randomization Individuals will be blinded to their randomization assignment.

[figure not shown]
randomized will be considered enrolled in the study.

[figure not shown]
The group to which each subject is randomly assigned will remain concealed from the subject and the blinded evaluator until after Visit 11, but the randomization assignment will be made known to the unblinded study staff. The randomization assignment may be revealed early if considered medically necessary by the investigator.

[figure not shown]

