### **5.2.10** Exploratory Analyses

### 6.2 Full Analysis Set

The Full Analysis Set (using a modified Intent to Treat approach) will include all subjects who sign a consent form, are randomized, and continue to meet eligibility criteria prior to the time of the lead placement procedure. All patients implanted with at least 1 lead with available data in weeks 5-8 will be analyzed according to the treatment group to which they were randomized.

Subjects who had a partial knee replacement or a revision knee replacement are excluded

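### SAP 6.2 applies a further eligibility condition after randomization to the primary analysis set, although Protocol 4.3 makes eligibility final before it

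*Protocol*

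**What the plan says.** Protocol 4.3 fixes the order of events: "Subjects will be randomized at the start of Visit 2, after final eligibility is verified and before lead placement procedures begin". Protocol 4.2.5 and the Randomized row of SAP Table 1 agree, since both treat a randomized subject as one who has already met all the eligibility criteria.

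SAP 6.2 then defines the Full Analysis Set as subjects who sign consent, "are randomized, and continue to meet eligibility criteria prior to the time of the lead placement procedure". SAP 5.0 makes this set the primary one for formal testing. The next sentence of 6.2 adds two further conditions for analysis: at least one lead implanted, and data available in Weeks 5-8.

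On knowledge of the assignment, Protocol 5.2.1 says that "the randomization assignment will be made known to the unblinded study staff". The text that follows it has subjects prepared for lead placement after assignment.

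The timing labels of the additional criteria differ. The inclusion items are headed "Additional inclusion criteria (assessed prior to randomization". The pregnancy exclusion is headed "Additional exclusion criteria (assessed before lead placement" in Protocol 4.2.1.4 and "Additional Exclusion Criteria (assessed before PNS" in the synopsis. Protocol 5.2 says that "individuals who qualify for lead placement (i.e., meet the additional inclusion and exclusion criteria) will return to the clinic" for Visit 2.

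**The concern.** If eligibility is final before randomization, a second eligibility condition on randomized subjects has no work left to do, except to remove someone because of a change or a judgement that came after assignment. By then part of the site team knows the group. Several exclusion criteria in Protocol 4.2.1.3 rest on the investigator's opinion (increased risk, anticoagulation, any other interfering condition), so the judgement is not always mechanical. An exclusion of this kind can differ between arms without anyone intending it, and it acts on the set that carries the confirmatory test. Blinding of the subject and of the evaluator does not protect against it.

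The pregnancy label matters less. It is tied to lead placement and not to randomization, so a site could run the test after assignment and still comply with the heading.

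**Working it through.** **1. The passages side by side**

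| Place | Eligibility condition | Relative to assignment |
|---|---|---|
| Protocol 4.3 | Final eligibility verified | Before |
| Protocol 4.2.5; SAP Table 1 | All criteria met | Before |
| Protocol 5.2 | Additional criteria met, then return for Visit 2 | Before |
| Protocol 4.2.1.2 | Additional inclusion criteria | Before (stated) |
| Protocol 4.2.1.4; synopsis | Pregnancy | Before lead placement / before PNS; order against randomization not stated |
| SAP 6.2 | Eligibility must continue up to lead placement | Extends past assignment |

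Only the last row applies a condition to subjects already randomized. There are two readings. If eligibility is final before assignment, the clause either repeats Protocol 4.3 and can go, or it removes subjects on something that arose afterwards. If eligibility is not final at assignment, the clause contradicts Protocol 4.3 and SAP Table 1. Both readings call for a correction.

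The pregnancy rows do not conflict with the rest: a test done before randomization satisfies all of them.

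**2. Sensitivity of the primary test**

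The sample size and its rationale are not visible in the public text, so there is no plan figure to reproduce. The test is Fisher's exact, two-sided at 0.05 (SAP 4.0 and 5.1). Its p-value is the sum of the hypergeometric probabilities, with margins fixed, of all tables no more likely than the one observed. Assumed for illustration: 50 per arm, with 19 and 10 successes.

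| Removed after randomization | Active | Sham | p |
|---|---|---|---|
| None | 19/50 | 10/50 | 0.0769 |
| 1 active failure | 19/49 | 10/50 | 0.0486 |
| 3 active failures | 19/47 | 10/50 | 0.0449 |
| 2 failures and 1 success, active | 18/47 | 10/50 | 0.072 |
| 3 failures from each arm | 19/47 | 10/47 | 0.073 |

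The result crosses 0.05 only where removal is one-sided and confined to failures.

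**3. False positives under a true null**

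For *n* per arm and a common success rate *p*, the rejection rate is the sum over (a, b) of Bin(a; n, p) × Bin(b; n, p) × 1[Fisher p < 0.05], after *k* would-be failures are taken out of the active arm. Each cell gives total rejection / rejection favouring active, in percent.

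| n, p | k = 0 | 4% removed | 8% removed |
|---|---|---|---|
| 25, 0.2 | 2.2 / 1.1 | 3.4 / 2.3 | 3.9 / 2.7 |
| 25, 0.3 | 2.3 / 1.1 | 3.5 / 2.4 | 3.8 / 2.7 |
| 50, 0.2 | 2.8 / 1.4 | 3.9 / 2.5 | 4.0 / 2.8 |
| 50, 0.3 | 3.1 / 1.5 | 4.0 / 2.5 | 5.0 / 4.0 |
| 75, 0.2 | 3.1 / 1.5 | 4.2 / 2.7 | 4.8 / 3.8 |
| 75, 0.3 | 3.3 / 1.6 | 4.3 / 2.8 | 5.3 / 4.4 |

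Here 4% is 1, 2 or 3 subjects and 8% is 2, 4 or 6. The nominal rate favouring active is 0.05/2 = 2.5%. Fisher's test starts below that, so selective removal of 4% uses up the margin and 8% exceeds it in every row, reaching 4.4% at most.

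**The case against.** The sponsor can fairly answer that the documents already put eligibility first, in four places, and that SAP 6.2 only tidies up a short interval within one visit. Pregnancy is a laboratory result and leaves little room for judgement by arm. Much of the Visit 2 text is not visible, and neither is part of the text around SAP 6.2, so a blinded review step could sit there. No outcome is known before lead placement, so nobody can pick out failures as the worst case supposes. Most of this stands, and it limits the size of the point. It does not explain why the primary set needs an eligibility condition on subjects already randomized.

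Three stronger readings are tempting, and the documents do not support them.

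- A reader might infer that pregnancy is decided after randomization. The heading sets a deadline that an earlier test also meets, and Protocol 4.2.5, 4.3 and 5.2 with SAP Table 1 all point to an earlier test.
- A reader might infer that a subject who changed analgesic during the baseline diary will pass Visit 2 unchecked, because the synopsis ties the general exclusions to Visit 1 and Protocol 5.2 names only the additional criteria. Protocol 5.21 lists a Visit 2 Screening step whose content is not visible, so a missing re-check cannot be shown.
- A reader might infer that unblinded staff decide continued eligibility. The documents say that they learn the assignment. The visible text gives neither the exact moment nor the person who judges eligibility.

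**Conclusion.** The point holds for SAP 6.2 set against Protocol 4.3. The primary analysis population carries an eligibility condition that runs past randomization, assignment is known to part of the staff, and no blinded judge is named in the visible text. The pregnancy label is a secondary ambiguity.

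The impact is probably small. The interval is short, few subjects should be affected, and the documents give no sign of selective removal. The Fisher figures and the enumerated error rates rest on assumed arm sizes and success rates and on perfectly selective removal from one arm. They show how little it takes to move the test and are not a forecast. The change is still worth making, because it concerns the confirmatory set and costs almost nothing.

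**What to change.** 1. In Protocol 4.2.1.4 and the matching synopsis row, align the timing with 4.3. State in 5.2 that all eligibility checks, including the pregnancy test and any re-confirmation of criteria that can change after Visit 1, are completed at Visit 2 before the assignment is opened. If a Visit 2 screening step already does this, cite it.
2. In SAP 6.2, delete the continued-eligibility clause. If the sponsor wishes to keep an exclusion, limit it to criteria whose facts predate randomization, judged by someone blinded to assignment and applied alike in both arms. If such a review already exists in text not visible here, refer to it in 6.2.
3. Report by arm any randomized subject left out on eligibility grounds, with the reason.

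This governs who is counted in the primary analysis and not how any subject is managed. It will not by itself retain every randomized primary-TKR subject: the lead and Weeks 5-8 data conditions in the next sentence of SAP 6.2 remain and need separate treatment.

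The cost is a few sentences in each document and possibly a changed order of steps within one visit. A few more subjects may fail screening at Visit 2 before randomization.
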